9.2.3 Supplementary Analysis

The primary efficacy analysis described in Section 9.2.1 will be repeated using the mITT and PP analysis sets on study eye only.

Descriptive summaries of change from Baseline in the proptosis for study eye and fellow eye at each scheduled visit will be provided by treatment group for each treatment period using the mITT and PP analysis sets.

9.2.4 Subgroup Analysis

The primary efficacy endpoint will be evaluated for subgroups of interest, including:

- Race (White, Black or African American, Asian, Other)
- Tobacco use status (Non-user, User)
- Age (<65 years, >=65 years)
- Sex (Male, Female)

For race, if the number of patients in any of the race groups is less than 5, we will pool “Black or African American”, “Asian”, “Other” into “Non-White”. For other variables, if the number of patients is less than 5 in any subgroup, then subgroup analysis will not be performed. For tobacco use status, tobacco uses of “Never” or “Former” will be grouped as tobacco “Non-users”, and tobacco uses of “Current” will be considered tobacco “Users” on the substance use eCRF.

9.2.5 Exploratory Analysis

9.3 Other Efficacy Endpoints

Inferential testing on other efficacy endpoints will be made only when the primary efficacy endpoint reaches statistical significance at 0.05 (two-sided) in favor of TEPEZZA. Other efficacy endpoints (with the main analyses defined in the study eye as appropriate) will be analyzed using the ITT analysis set in a hierarchical manner presented in the order in Section 5.6. For each outcome measure, TEPEZZA will be tested against placebo at the two-sided 0.05 significance level only if the test statistic was statistically significantly in favor of TEPEZZA for the outcome measure preceding it in the hierarchical order.

9.3.1 Proptosis Responder Rate at Week 24

The proptosis responder rate is defined as the percentage of patients with a ≥ 2 -mm reduction from Baseline in proptosis in the study eye, without deterioration [≥ 2 -mm increase] of proptosis in the fellow eye at each scheduled visit.

Population	ITT Analysis Set defined as all patients who were randomized in the trial
Endpoint	
Proportion of patients who have achieved the proptosis response rate at Week 24.
 
The proptosis responder rate at Week 24 is defined as the percentage of patients with a ≥ 2-mm reduction from Baseline in proptosis in the study eye, without deterioration (≥ 2-mm increase) of proptosis in the fellow eye at Week 24.

ICE	Discontinued from treatment early
Population-level Summary	Difference (TEPEZZA minus placebo) in proptosis responder rates at Week 24 between the treatment groups

9.3.1.1 Primary Analysis Method

Patients whose Week 24 evaluation is missing will be considered treatment failures (non-responders). Difference in proptosis responder rates at Week 24 for study eye between the two treatment groups (TEPEZZA minus placebo) on the ITT analysis set will be compared using a two-sided Fisher Exact test. A 95% exact CI around the proportion difference between the two treatment groups will be provided. The same analysis will be repeated using observed results. In this analysis, only patients with a non-missing evaluation at Week 24 are included.

Further, the definition of responder will be applied for each scheduled visit in double-masked treatment period and the analysis of risk difference will be performed, considering patients missing the evaluations as treatment failures (non-responders) and separately considering the observed results only. In order to investigate the effect of treatment on the fellow eye, the analysis for fellow eye will be conducted. The same analyses will be repeated to include

responder status at each scheduled visit in open-label treatment period, but no analysis of risk difference will be performed.

Line plot of proptosis responder rate over time by treatment group for the study eye based on the ITT analysis set will be provided for each treatment period.

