5.1 Sample Size

A total of 57 patients (38 in the TEPEZZA group and 19 in the placebo group) will be enrolled in the trial to detect at least a 2-mm mean difference between the 2 treatment groups in the change from Baseline of proptosis values at Week 24 in order to have 81% power at the two-sided 0.05 level of significance. The sample size was determined assuming that the mean difference in

proptosis change between the 2 groups is at least 2.0 mm (clinically relevant) and the standard deviation of proptosis change values is 2.5 for both groups (larger than the observed in Phase 2 and Phase 3 active TED trials).

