5.3 Analysis Set

5.3.1 Intent-to-Treat (ITT)

The ITT analysis set is comprised of all patients who are randomized to receive study drug (either TEPEZZA or placebo). This will be the primary analysis set for efficacy analysis for each treatment period. Patients will be analyzed according to their randomized treatment assignment.

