8.4.2 Treatment Compliance and Modifications

All doses of study drug will be administered and recorded by study site personnel, and any deviations from the dosing schedule will be entered into the patient's eCRF. The study drug administration records will be listed for each patient with study drug administered, start date and time, stop date and time, dose, if there's any dose interruptions incompleteness and reasons.

Summaries will be provided for the count and percentages of patients with each of the following by treatment group for each treatment period:

- Planned doses that were not administered completely
- Infusion interruptions

Planned TEPEZZA doses that were not administered completely and infusion interruptions to TEPEZZA in double-masked treatment period and open-label treatment period will be summarized by treatment group.

9. Efficacy Analysis

Efficacy analysis will be conducted for the double-masked period (as the primary analysis) and open-label period (as the follow-up analysis) separately based on the ITT analysis set. Efficacy analysis results from the primary analysis (i.e., based on the data collected during the double-masked period) will be used for comparison between the two treatment groups. Both study and fellow eyes will be used for the efficacy analyses during the primary analysis, but the statistical inference will be made based on study eye analysis results only. For the follow-up analysis, which will be conducted using subsequent assessments collected during the open-label treatment period, only descriptive summaries of efficacy analysis results will be provided.

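### As written, one of the two planned open-label responder summaries counts patients who never enter the open-label period as failures at Weeks 27 to 48; the denominator should be patients who entered

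*SAP*

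**What the plan says.** Five parts of the SAP combine here.

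- **Analysis set.** Section 5.3.1 defines ITT as everyone randomized and adds: "This will be the primary analysis set for efficacy analysis for each treatment period". The opening of Section 9 repeats this for the "open-label period (as the follow-up analysis) separately based on the ITT analysis set".
- **Denominator.** Section 5 (General Statistical Considerations) bases percentages on all patients of the arm within the analysis set, those with missing values included, unless something else is specified.
- **Responder analysis.** Section 9.3.1.1 applies the responder definition at each double-masked visit in two versions: missing counted as non-response, and observed results only. The same analyses are then extended to "responder status at each scheduled visit in open-label treatment period, but no analysis of risk difference will be performed". It also plans a figure: "Line plot of proptosis responder rate over time by treatment group for the study eye based on the ITT analysis set will be provided", one for each treatment period.
- **Who enters.** Under Section 3.1, only proptosis non-responders who completed the double-masked period may choose open-label TEPEZZA. Responders, and non-responders who decline, go to a 30-day follow-up contact.
- **Visit windows.** The footnote to Table 1 in Section 5.4.3 maps everything from Day 149 onward to Week 24 for patients who do not enter. Their Week 27 to Week 48 cells are therefore empty by design.

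None of the five analysis sets in Section 5.3 (ITT, mITT, PP, Safety, PK) is limited to patients who entered the open-label period.

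**The concern.** A Week 24 responder cannot have an open-label proptosis value. If the set is all randomized patients and missing means non-response, that patient appears as a failure at every open-label visit, although the reason for the empty cell is that treatment worked. Non-responders who decline and patients who left early are handled in the same way.

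Section 4.3 presents open-label results by the treatment received in the double-masked period, so the effect shows up as a difference between the original arms. The more patients an arm has who respond by Week 24, the lower its open-label rate can be. A reader of that table could take a feature of the denominator for a treatment result.

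**Working it through.** **The plan's own figure.** The only design figure nearby is the sample size, and it is not in dispute. Inputs from SAP Section 5.1: "A total of 57 patients (38 in the TEPEZZA group and 19 in the placebo group) will be enrolled"; difference 2.0 mm; "standard deviation of proptosis change values is 2.5 for both groups"; two-sided 0.05; stated power 81%.

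- Standard error = 2.5 × √(1/38 + 1/19) = 0.702.
- Power (normal approximation) = Φ(2.0/0.702 − 1.96) = Φ(0.887) = 81.3%.
- A t-test with 55 degrees of freedom gives 79.9%.

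The stated 81% reproduces. The arm sizes of 38 and 19 are used below.

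**Ceiling on the open-label rate.** Let N be the arm size and R the number of Week 24 responders. At most N − R patients can enter. On full ITT with missing as non-response, the denominator stays N, so the rate cannot exceed (N − R)/N even if every non-responder enters and responds.

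**Assumed values of R.** The documents give no responder rates. I assume a normal change score with SD 2.5 mm and a 2.0 mm difference (SAP 5.1). For the untreated mean I take −0.48 mm, which Protocol Section 7.2 gives for its inactive-disease placebo subgroup, and vary it from 0 to −1.0 mm. The fellow-eye condition is ignored. With untreated mean m, the probability of a reduction of at least 2 mm is Φ((−2 − m)/2.5) on placebo and Φ(−m/2.5) on TEPEZZA.

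| Untreated mean m | TEPEZZA responders of 38 | Ceiling | Placebo responders of 19 | Ceiling |
|---|---|---|---|---|
| 0 | 50.0% → 19 | 19/38 = 50.0% | 21.2% → 4 | 15/19 = 78.9% |
| −0.48 mm | 57.6% → 22 | 16/38 = 42.1% | 27.2% → 5 | 14/19 = 73.7% |
| −1.0 mm | 65.5% → 25 | 13/38 = 34.2% | 34.5% → 7 | 12/19 = 63.2% |

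**Same data, two denominators.** Take the middle row, let every non-responder enter, and let half of the entrants in each arm respond at some open-label visit.

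- Denominator of entrants: 8/16 = 50% (TEPEZZA first) and 7/14 = 50% (placebo first).
- Full ITT, missing as non-response: 8/38 = 21.1% and 7/19 = 36.8%.

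The arms are equal among entrants, yet differ by 36.8 − 21.1 = 15.7 percentage points on the ITT denominator.

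**What the observed-only version adds.** Suppose 4 of the 16 TEPEZZA-first entrants have no value at the visit and 8 respond. Observed-only gives 8/12 = 67%, full ITT gives 8/38 = 21%, and entrants with missing as non-response gives 8/16 = 50%. Neither written version produces the last figure.

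**The case against.** The strongest reply is that entrants were probably meant all along.

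- Section 4.3 bases open-label efficacy on data collected in that period.
- Section 5.4.2 uses TEPEZZA Baseline for that period, and this does not exist for a placebo patient who never receives TEPEZZA.
- Section 6.1 counts disposition on patients who entered each period.
- The schedule in Section 15.1 labels the open-label columns as belonging to non-responders who chose to enter, so a Week 24 responder arguably has no scheduled evaluation to miss.
- The general denominator rule yields where something else is specified, and the table shells are not public.

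This makes a deliberate full-ITT choice unlikely. It does not settle the denominator: none of these places sets it for the responder rate, while Sections 5, 5.3.1 and 9 all point to everyone randomized.

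A second reply is that Section 9.3.1.1 also carries the observed-only version to the open-label visits, and that version leaves out patients who never enter. This stands. It limits the point to one of the two summaries, and possibly the plot. It is not a full substitute, because it also loses entrants who later withdraw.

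A third reply also stands: Section 4.3 makes all open-label results descriptive, without modeling or tests, and Section 9.3.1.1 rules out a risk difference there.

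**Conclusion.** The point holds in a limited form and is minor. Followed literally, the missing-as-non-response summary at Weeks 27 to 48 counts every patient who never enters as a failure. Under the assumptions above, its ceiling is 50% to 34% for the original TEPEZZA arm and 79% to 63% for the original placebo arm. These percentages rest on assumed Week 24 responder counts and on full entry and full response among non-responders; lower uptake would lower them. The formula and its direction need no such assumption: more Week 24 responders in an arm means a lower ceiling.

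Three stronger readings are tempting and are not supported.

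- A reader might infer that later response under open-label treatment could not be read at all. The observed-only summary would still show it among entrants with data.
- A reader might infer that the line plot will show a false collapse after Week 24. Section 9.3.1.1 does not say which missing-data rule the plot uses, and it plans one plot per period, with none running across Week 24.
- A reader might infer that all open-label efficacy output is distorted. Section 9.1 analyzes continuous endpoints on observed data, so no absent patient becomes a failure there.

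The Week 24 primary analysis and the hierarchical tests are unaffected.

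**What to change.** Add to SAP Section 5.3 an open-label analysis set: ITT patients who received at least one open-label TEPEZZA infusion. Use it as the denominator for open-label responder rates and for the open-label responder line plot. Apply missing-as-non-response only within that set, keep the observed-only version beside it, and state in Section 9.3.1.1 which missing-data rule the plot follows.

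The cost is one definition, a sentence or two in Section 9.3.1.1, and a changed denominator in the open-label responder shells. No new data are needed and nothing in the Week 24 analysis changes. If the shells already use entrants, only the SAP text needs to be brought into line.

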9.3.1.2 Sensitivity Analysis Method

CCI [REDACTED]
[REDACTED]
[REDACTED]
[REDACTED]
[REDACTED]
[REDACTED]
[REDACTED]
[REDACTED]
• [REDACTED]
• [REDACTED]
• [REDACTED]
• [REDACTED]
[REDACTED]

9.3.2 Change from Baseline at Week 24 in the GO-QoL Questionnaire Appearance and Visual Functioning Subscales

The GO-QoL questionnaire (see Protocol section 17.5) has CCI [REDACTED]
[REDACTED]
[REDACTED]
[REDACTED]
[REDACTED]
[REDACTED]

CCI

9.3.3 CCI

CCI

• [REDACTED]

- [REDACTED]
- [REDACTED]
- [REDACTED]
- [REDACTED]

[REDACTED]

CCI

The same primary analyses described in Section 9.3.1.1 will be repeated for this endpoint.

9.4 Exploratory Endpoints

9.4.1 CCI

CCI

10. Safety Analysis

Safety parameters include monitoring of TEAEs, SAEs, vital sign measurements, laboratory tests and visual acuity.

Safety data will be summarized and listed with no statistical hypothesis testing performed. Continuous variables will be summarized using the mean, the SD, median, 25th percentile, 75th percentile, minimum value, and maximum value. Categorical variables will be summarized using

frequency counts and percentages. All safety summaries and analyses will be conducted separately for each treatment period based on the safety analysis set.

10.1 Adverse Events

Adverse events will be coded using MedDRA version 24.0. AEs that occur during Screening and prior to dosing on Day 1 will be considered pre-treatment AEs. TEAEs for the double-masked treatment period is defined as AEs with onset date on or after the first dose of study drug during the double-masked treatment period prior to receiving the first dose of TEPEZZA during open-label treatment period for patients who entered open-label treatment period, or through 3 weeks (21 days) after the last dose of study drug during the double-masked treatment period for patients who did not enter open-label treatment period. TEAEs for open-label treatment period defined as AEs with onset date on or after first dose of TEPEZZA during the open-label treatment period through 3 weeks (21 days) after last dose of TEPEZZA during the open-label treatment period. All analyses for TEAEs will be split to TEAEs reported during the double-masked treatment period and open-label treatment period separately. The follow-up AE reporting period begins 3 weeks (21 days) after the last dose of study drug through completion of the follow-up period.

An overall summary of all TEAEs including the number and percentage of patients experiencing at least one occurrence of a TEAE, serious TEAEs, treatment-related TEAEs, treatment-related serious TEAEs, TEAEs resulting in study drug discontinuation, TEAEs of special interest, TEAEs leading to death along with the summary of National Cancer Institute Common Terminology Criteria for Adverse Events (NCI-CTCAE) grade 3 or higher will be provided.

Additionally, AEs and SAEs reported during the follow-up period after each treatment period will be presented by SOC and PT separately.

All AEs, AEs with CTCAE Grade 3 or higher, SAEs, AEs leading to discontinuation of study drug, AE of special interest, and deaths will be presented in separate by-subject listings.

Signs and symptoms associated with Infusion reaction and anaphylaxis will be recorded and included in a by-subject listing.

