At the end of the double-masked Treatment Period (Week 24), all patients will be assessed for treatment response: proptosis responders (study eye has  $\geq 2$ -mm reduction in proptosis from Baseline without deterioration [ $\geq 2$ -mm increase in proptosis] in fellow eye) or proptosis non-responders (study eye has  $< 2$ -mm reduction in proptosis). Proptosis non-responders who have completed the double-masked Treatment Period may choose to receive 8 infusions of TEPEZZA (10 mg/kg for the first infusion and 20 mg/kg for the remaining 7 infusions) in an open-label fashion q3W at Weeks 24, 27, 30, 33, 36, 39, 42 and 45. These patients will return to the clinic at Week 48 for End-of-Treatment assessments, and patients will be contacted by phone/email 30 days after the Week 48 Visit for safety assessment. Proptosis responders, as well as non-responders who choose not to receive TEPEZZA in an open-label fashion, will enter a 30-day Follow-up Period, during which trial drug will not be administered. These patients will be contacted by phone/email 30 days after the Week 24 Visit for safety assessment.

Patients who prematurely discontinue trial drug dosing prior to Week 21 of the double-masked Treatment Period or prior to Week 45 of the open-label Treatment Period will return to the clinic, undergo the scheduled End-of-Treatment assessments (with the exception of the **CCI** [ ] and enter the Follow-up Period, provided such continued participation will not detrimentally affect the health, safety and welfare of the patient per Investigator determination.

An overview of the trial design is presented in [Figure 9.1](#), and details of trial activities are presented in [Section 2.1, Schedule of Assessments](#).

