4.2 Primary Analysis

The primary analysis of efficacy, safety and tolerability is planned after all patients complete the Week 24 visit assessments in the double-masked treatment period or terminate early from the study prior to Week 24. Efficacy analyses are based on data collected from the Screening visit through Week 24 visit. Safety analyses are based on data collected up to last patient’s Week 24 visit date.

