4.3 Follow-up Analysis

The follow-up analysis is planned at the end of the trial after all patients complete the 30-day follow-up period or terminate early from the study during the follow-up period. The follow-up analysis will focus on the open-label treatment period. For the open-label treatment period,

1. Only descriptive summaries will be provided and no statistical modeling or statistical hypothesis tests will be performed.
2. Neither sensitivity nor supplementary analysis will be performed.
3. Analysis results will be presented by the treatment patients received during the double-masked treatment period.

Efficacy analyses are based on data collected from open-label treatment period. Safety analyses are based on data collected from open-label treatment period as well as 30-day follow-up data that are not included in the primary analysis.

5 General Statistical Considerations

The primary efficacy endpoint will be tested at the level of significance of 0.05 two-sided. Other efficacy endpoints will be tested in a sequential order as listed in Section 3.2.2 only when statistical significance is achieved for the primary efficacy endpoint and the other preceding endpoint in the prespecified order is statistically significant at the 0.05 significant level (two-sided).

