5.5.3 Adverse Events

For adverse events with incomplete dates, the following rules will be used to impute start and/or stop dates for the sole purpose of determining whether if an AE is treatment emergent. Imputed dates will not appear in the data listings.

For partial or missing AE start dates:

- If day is missing, and the month and year match the month and the year of the first dose date, the day of the first dose date will be imputed and the AE will be considered treatment emergent. Otherwise, the first of the month will be used and the treatment-emergent status will be assessed relative to the dosing start date.
- If the day and month are missing, and the year matches the year of the first dose date, the month and the day of the first dose date will be imputed, and the AE will be considered treatment emergent. Otherwise, January 1 will be used and the treatment emergent status will be assessed relative to the dosing start date.
- If the start date is completely missing, the AE will be considered treatment emergent unless the stop date is complete and prior to the first dose or provides enough partial information to rule out a treatment-emergent status.
- If the stop date is complete and the imputed start date is after the actual stop date, then the start date will be imputed as the stop date and the treatment-emergent status will be assessed relative to the dosing start date.

Any missing intensity assessments for AEs will be imputed as “severe” and any missing relationship to study drug will be considered “related” for summary purposes.

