10.1.3 Severity of Adverse Event

The severity of AEs will be evaluated by the NCI-CTCAE (v4.03). the grade will be assessed by the investigator as mild (Grade 1), moderate (Grade 2), severe (Grade 3), life-threatening (Grade 4), or fatal (Grade 5).

For AE grade tables, the patient will be counted once with the highest-grade event if he/she experiences more than one event under given SOC or PT level.

A summary of CTCAE Grade 3 or higher TEAEs by SOC and PT will be presented by treatment group.

Summary of all TEAEs and SAEs respectively will be presented SOC, PT and maximum severity of AEs.

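### TEAEs are assigned to a period by onset date alone, so unless an eCRF rule splits the record, an AE that worsens on open-label TEPEZZA after starting in the masked period is left out of the open-label summaries

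*SAP*

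**What the plan says.** SAP 10.1 gives two definitions, and both turn on onset. For the first period: "TEAEs for the double-masked treatment period is defined as AEs with onset date on or after the first dose of study drug". That window closes at the first open-label dose, or 21 days after the last masked dose for patients who do not continue. For the second: "TEAEs for open-label treatment period defined as AEs with onset date on or after first dose of TEPEZZA during the open-label treatment period", closing 21 days after the last open-label dose. The same section splits every TEAE analysis by period, and SAP 10 adds: "All safety summaries and analyses will be conducted separately for each treatment period based on the safety analysis set".

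SAP 10.1.3 counts a patient once per term at the highest grade and plans a severity table: "Summary of all TEAEs and SAEs respectively will be presented SOC, PT and maximum severity of AEs". It does not limit the grade to the one reached in the period being tabulated.

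Protocol 9.1 sets out who crosses the boundary: "Proptosis non-responders who have completed the double-masked Treatment Period may choose to receive 8 infusions of TEPEZZA". This is open to non-responders from both arms. Under Protocol 9.5.6.2.5 the first open-label infusion is given at the Week 24 visit, so there is no gap between the periods.

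**The concern.** An AE that is mild in the masked period, still ongoing at Week 24 and worse during open-label dosing has its onset in the masked period. Under the onset rule it is a masked-period TEAE only. The worsening on TEPEZZA does not enter the open-label tables unless it has its own record with its own onset date.

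This matters most for former placebo patients, for whom open label is first exposure to the drug. Worsening of an existing complaint at first exposure is something the open-label tables should show. Hearing impairment is an example: it is an AESI, it has no separate test-result table in the SAP, and Protocol 9.5.3.1.1.5 makes the audiogram optional.

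The SAP handles the same boundary differently for medications. Under SAP 8.1, a drug started in the masked period and continued into open label counts in both periods. AEs have no parallel rule.

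**Working it through.** The plan states no figure on this point. The check is a reading of the AE rules, one worked record and a scale calculation.

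**1. Is there a worsening rule anywhere?**
- SAP 10.1: onset date only, in both periods.
- Protocol 9.5.3.1.1.1: worsening of pre-existing conditions and clear exacerbation of chronic conditions are to be recorded. This most naturally concerns conditions present at entry. It sets no rule for an AE already on the eCRF.
- Protocol 9.5.3.1.2, 9.5.3.1.3 and 9.5.3.1.6 (documentation, intensity, follow-up): nothing says that a change of grade opens a new record.
- Protocol 10 (source documents): AE start and stop dates are listed, but no date of grade change.
- Protocol 13: data entry is deferred to a data management plan that is not among the documents.

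**2. Worked record (hypothetical AE days).** Onset is Day 100 at Grade 1. The first open-label dose is on Day 169, the Week 24 target in SAP Table 1. The AE worsens to Grade 3 on Day 200. The last planned open-label dose is at Week 45, Day 45 × 7 + 1 = 316, so the open-label window runs to Day 316 + 21 = 337. Day 200 lies inside it.

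| Record keeping | Masked-period maximum grade | Open-label TEAEs |
|---|---|---|
| One record, top grade kept | 3 | 0 |
| New record at worsening | 1 | 1, at Grade 3 |

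The AE counts once in masked-period incidence either way. What changes is the open-label count and, in the first row, the masked-period severity.

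**3. When could the later grade reach the masked-period table?** On the data cut, SAP 4.2 says: "Safety analyses are based on data collected up to last patient’s Week 24 visit date". Patients enrolled early can have open-label data by then. In the worked record, the cut would have to fall at least 200 − 169 = 31 days after that patient's first open-label dose. All of these must hold:
- the patient enters open label;
- the AE is still ongoing at the first open-label dose;
- its grade rises;
- the site keeps one record and overwrites the grade;
- this happens before the cut.

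SAP 4.3 describes no rerun of the masked-period tables.

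**4. Scale.** Planned enrolment is 38 TEPEZZA and 19 placebo (SAP 5.1). For the open-label tables, SAP 4.3 states: "Analysis results will be presented by the treatment patients received during the double-masked treatment period". Only non-responders who choose treatment enter, so the columns hold at most 19 and 38 patients.
- Former placebo: 1/19 = 5.3%, so one omitted patient is at least 5.3 points.
- Former TEPEZZA: 1/38 = 2.6%, so one omitted patient is at least 2.6 points.

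A patient drops out of a preferred-term row only if no other event with that term began in open label. In the masked-period table, 1/19 and 1/38 apply only to a severity row. A count of affected patients would need the share entering open label, the share with an ongoing AE and the share worsening. The documents give none of these.

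**The case against.** The strongest reply is that the defect depends on a document we cannot see. If the eCRF completion rules already open a new record at each change of grade, the onset rule works as it stands. That is correct, and the point is conditional on it. The SAP neither cites such a rule nor depends on one explicitly, so the gap in the written plan remains.

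The loss is also bounded:
- The by-subject listings in SAP 10.1 (all AEs, Grade 3 or higher, SAEs, discontinuations, AESIs, deaths) are not restricted to TEAEs.
- The SAE table in SAP 10.1.4 has no TEAE limit.
- SAP 10.2 and 10.3 provide laboratory tables including glucose by grade, a weight-loss table and a hypertension shift table.
- Safety is descriptive.

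All of this stands. The listings preserve the data, but they do not restore the event to the open-label summaries.

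A reader might take SAP 5.5.3, where "the treatment-emergent status will be assessed relative to the dosing start date", as a second onset-only definition. It is an imputation rule for incomplete dates and adds little. A reader might also infer that worsening makes the masked-period comparison of TEAE rates wrong. It does not: an AE that began in the masked period is correctly counted there. Finally, a reader might treat transfer of later grades into the masked-period table as routine. The conditions in the working show that it is a less likely side effect.

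**Conclusion.** The point holds in a conditional form. As written, the onset-only rule leaves worsening on open-label TEPEZZA of an AE that began in the masked period out of the open-label TEAE, AESI and Grade 3 or higher summaries for that event, in either arm, unless an eCRF rule outside the documents splits the record. The documents do not show that any event will be miscounted.

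Overstatement of masked-period maximum severity is possible but secondary, and rests on a single overwritten record before the data cut. Masked-period incidence and all hypothesis tests are unaffected. The number of patients is probably small and cannot be estimated. The percentages in the working are for scale only and assume planned enrolment. This is a cheap improvement to the safety reporting and does not threaten the trial's conclusions.

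**What to change.** In SAP 10.1, define a TEAE for each period as an AE with onset, or with worsening in grade or seriousness, on or after the first dose of that period and within the existing window. Apply it by having sites enter worsening of an ongoing AE as a new record dated at the change. If an eCRF rule already requires this, cite it. In SAP 10.1.3, tabulate only the grade reached within the period.

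The cost is a few sentences in the SAP and an eCRF completion instruction, or one sentence referring to an existing rule. A few events will be counted in both periods, as SAP 8.1 already accepts for medications, and TEAE counts may rise slightly. Records already entered may need site queries to date the grade change, because the source items listed in Protocol 10 do not include that date.
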